# 2. PATIENT POPULATION

# 2.1. Population (Analysis Set) Definitions

The following patient populations (analysis sets) will be evaluated and used for presentation and analysis of the data:

- Evaluable Analysis Set: All patients who have received at least a single dose of study drug and have a non-missing serum TTR result at Month 6 (Week 26) visit.
- Safety Analysis Set: All patients who received at least a single dose of study drug.
- PK Analysis Set: All patients who received at least a single dose of study drug and have at least 1 postdose blood sample for PK parameters and who have evaluable PK data.

The primary efficacy endpoint will be analyzed using the Evaluable Analysis Set. All secondary and exploratory efficacy endpoints will be analyzed using the Evaluable Analysis Set and Safety Analysis Set (note: if these 2 analysis sets are identical then secondary and exploratory efficacy endpoints will be analyzed using only the Evaluable Analysis Set). Safety will be analyzed using the Safety Analysis Set. The PK Analysis Set will be used to conduct PK analyses. PK analyses are described in a separate PK analysis plan.

# 2.2. Protocol Violations

All protocol deviations will be presented in a data listing.

# **3. GENERAL STATISTICAL METHODS**

# **3.1.** Sample Size Justification

Approximately 12 patients will be enrolled in this study. For the estimation of sample size, a mean reduction of 88% in serum TTR has been observed from baseline to Day 35 with a standard deviation (SD) of 6% in healthy volunteers taking revusiran. If this study yields a mean reduction of 80% at 6 months with an SD of 6%, 12 patients would yield a 95% confidence interval (CI) of approximately 77% to 83%.

# **3.2.** General Methods

All data listings that contain an evaluation date will contain a relative study day (Rel Day). Pretreatment and on-treatment study days will be calculated relative to the day of the first dose of study medication which is designated as Day 0. The day preceding first dose is Day -1. The last day of study medication is designated with an "L" (e.g., Day 14L). Post-treatment study days are numbered relative to the last dose and are designated as Day 1P, Day 2P, etc.

All outputs will be incorporated into Microsoft Word or Excel files, or Adobe Acrobat PDF files, sorted and labeled according to the International Conference on Harmonisation (ICH) recommendations, and formatted to the appropriate page size(s).

For categorical variables, summary tabulations of the number and percentage of patients within each category (with a category for missing data) of the parameter will be presented. For continuous variables, descriptive statistics including the number of patients, mean, median, SD, minimum, and maximum values will be presented.

If assessments are collected in replicates (e.g., grip test, mNIS+7), then the average of the replicates will be used in the analyses.

# **3.3.** Computing Environment

All descriptive statistical analyses will be performed using SAS statistical software Version 9.3 (or later), unless otherwise noted. Medical history and AEs will be coded using the Medical Dictionary for Regulatory Activities (MedDRA) Version 18.0 (or later). Concomitant medications will be coded using the World Health Organization (WHO) Drug Dictionary March 2015 Version (or later).

### **3.4. Baseline Definitions**

Baseline will be defined as the measurement closest to and prior to the first administration of study drug for all safety assessments and clinical outcomes. For TTR and Vitamin A, baseline will be defined as the average of all pre-dose values (i.e., screening, screening/baseline, and baseline, as well as any values from unscheduled visits that occur prior to dosing on Day 1).

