Note: White boxes are visits to the clinical study centers; whereas, grey boxes are for dosing procedures that may be conducted at home. If, at any time during the study, a liver biopsy is performed per standard of care procedures, an optional evaluation of residual liver tissue may also be performed. Additionally, patients will be monitored for possible liver allograft rejection; any biopsies performed to rule out allograft rejection will be evaluated according to the Banff Working Group on Liver Allograft Pathology criteria, a set of consensus criteria for the causes of liver allograft dysfunction.

- ^a The Screening/Baseline visit must be performed within 21 days before the first dose of study drug (Day 0). The Baseline visit must be conducted at least 24 hours, but not more than 7 days, after the Screening/Baseline visit. In consultation with the Medical Monitor(s), the Investigator may re-screen a patient after a minimum of 5 days have elapsed from the last screening assessment.
- ^b The withdrawn patient will be asked to consent to either be contacted by telephone or to allow non-patient contact follow-up (eg, medical record check) for up to 18 months after enrolling in the study to document overall health status.
- ^c Dosing on Days 1, 2, 3, and 4 must be performed 24±4 hours after the preceding dose of study drug. After Day 7±1, study drug will be administered weekly (±2 days). A 14-day window is permitted for study visits after Month 2 (excluding study drug administration).
- ^d LFTs must be assessed within 14 days of Day 0 (Predose) and results must be known before the first dose of study drug. Other results from the clinical laboratory samples collected on Day 0 are not needed before dosing.
- ^e A complete medical history of FAP and OLT will be collected. An interval medical history will be collected during the Screening/Baseline and Baseline visits and only changes in medical history will be recorded. As part of the complete medical history, if available, the prior 6 months of LFTs will also be collected.
- ^f Vital signs include blood pressure, heart rate, oral body temperature, and respiratory rate. Vital signs will be measured in the seated or supine position (should be consistent for each patient), after the patient has rested comfortably for 10 minutes. Vital signs should be collected at each clinical study center visit.

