6.5. Administration

Beginning on Day 0, patients will receive 5 daily SC doses of 500 mg of revusiran administered as 2 injections. The same dose will be administered at Day 7 and then weekly from Week 2 through 18 months. Study drug will be administered at the clinical study center on Days 0 through 4 by qualified clinical study center staff under the supervision of the Investigator, or designee.

After Day 4 study drug may be administered at home by a healthcare professional trained in the administration of study drug or at the clinic. At the discretion of the Investigator, after the Month 6 dosing visit, and if the patient has not previously experienced any severe AE or SAEs considered related to the study drug within the previous 12 weeks, that the Investigator and Medical Monitor believe should preclude the patient from self-administration, patients/caregivers

may be trained by the Investigator or qualified clinical study center staff in the administration of the study drug, according to the protocol dosing requirements. If a severe AE or related SAE occurs, patients should not self-administer study drug for a 12-week period, unless prior approval is obtained from the Medical Monitor. The preferred region of SC injection is the abdomen. Optional additional regions include the upper arms and thighs. The site of injection within a given region will be rotated and recorded.

Detailed instructions can be found in the Pharmacy Manual.

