#### 1.2. Study Design

#### 1.2.1. Synopsis of Study Design

This is a multicenter, multinational, open-label study designed to evaluate the efficacy, safety, and PK of subcutaneously (SC) administered revusiran in patients with TTR-mediated FAP with disease progression post-OLT. It is anticipated that patients from approximately 5 clinical study centers will participate in this study.

Eligible, consenting patients will receive 5 daily doses of revusiran (Days 0 through 4) and a dose at Day 7, followed by once weekly doses for the duration of the study.

Visits will be held at the clinical study center for the following visits, as stated in the schedule of assessments in the protocol: Screening Period (Day -42 to Day -1), Predose Assessments (Day 0), and Daily Dosing (Days 0 through 4) as well as each month for the first 3 months, and approximately every 3 months through Month 18 (or Early Termination), and at the End of Study (EOS) (approximately 28 days after the last dose). The remaining study visits may be conducted at the clinical study center or in the patient's home.

The primary objective of this study will be evaluated by the collection of serum samples for the measurement of total TTR levels. TTR samples will be collected prior to study drug administration, and then assessed on a monthly basis for 3 months, approximately every 3 months thereafter, and at Early Termination.

Adverse events (AEs) will be collected throughout the treatment period and at the EOS visit.

Patients will participate in this study for approximately 21 months (inclusive of a 42-day screening period and a follow-up visit 28 days after the last dose of study drug) and will be treated with study drug for 18 months.

An independent Data Monitoring Committee (DMC) will be implemented for the study and will operate under a prespecified charter.

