## 3.11. Visit Windows

It is expected that all visits should occur according to the protocol schedule. All data will be tabulated per the evaluation visit as recorded on the eCRF even if the assessment is outside of the visit window.

Data collected at unscheduled visits will be included in by-patient data listings, but no assignment to a study visit will be made for the purpose of by-visit summary tabulations. However, unscheduled visits will be considered for computation of baseline values, as discussed in Section 3.4, and for inclusion in any categorical shift summaries (e.g., shift from baseline to "worst" post-baseline value).

The relative day of all dates will be presented in data listings.

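### SAP 3.4 sets the TTR and vitamin A baseline cut-off at the second dose instead of the first, and its visit list omits the Day 0 predose sample

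*SAP*

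**What the plan says.** SAP 3.4 has two sentences. The first, for safety assessments and clinical outcomes in general, takes the last measurement before the first administration of study drug. The second makes an exception for TTR and vitamin A, for which "baseline will be defined as the average of all pre-dose values". A parenthesis then spells this out as the screening, screening/baseline and baseline visits, "as well as any values from unscheduled visits that occur prior to dosing on Day 1". SAP 3.11 makes the clause on unscheduled values operative: "unscheduled visits will be considered for computation of baseline values, as discussed in Section 3.4".

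On day numbering, SAP 3.2 counts study days "relative to the day of the first dose of study medication which is designated as Day 0". Protocol 6.5 agrees: "Beginning on Day 0, patients will receive 5 daily SC doses". Footnote c of protocol Table 1 says that dosing on Days 1 to 4 "must be performed 24±4 hours after the preceding dose of study drug".

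On sampling, SAP 1.2.1 states that "TTR samples will be collected prior to study drug administration, and then assessed on a monthly basis for 3 months". It lists the Day 0 predose assessments separately from the screening period, which ends on Day -1.

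**The concern.** The second sentence of SAP 3.4 departs from its own general rule in two ways.

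- **Cut-off.** A value obtained after the Day 0 dose but before the Day 1 dose is post-treatment, yet the parenthesis admits it if the visit was unscheduled. The preceding sentence uses the correct anchor, so one short section contains two different cut-offs.
- **Visit list.** The list is introduced as a definition, not as examples, and it does not match the schedule of assessments. It names a visit with no TTR or vitamin A sample and omits the Day 0 predose sample.

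Baseline TTR is the denominator of the primary endpoint, the percent reduction at 6 months. A programmer who follows the general rule and one who follows the parenthesis could derive different baselines. On one literal reading, post-dose data enter the baseline. On another, vitamin A has no scheduled baseline value.

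**Working it through.** **1. Day numbering.** First dose: Day 0 (SAP 3.2, protocol 6.5). Day 1 dose: 24±4 hours later (Table 1, footnote c). The SAP 3.4 cut-off therefore falls 20 to 28 hours after the first dose.

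**2. Visit list against protocol Table 1 (pretreatment columns).**

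| Visit | Named in SAP 3.4 | TTR scheduled | Vitamin A scheduled |
|---|---|---|---|
| Screening | yes | no | no |
| Screening/Baseline | yes | yes | no |
| Baseline | yes | yes | no |
| Day 0 predose | no | yes | yes |

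The list captures 2 of 3 scheduled TTR samples and 0 of 1 scheduled vitamin A samples. Baseline cannot simply be read as Day 0 predose. Footnote a makes Baseline a separate visit, held 24 hours to 7 days after Screening/Baseline, and Table 1 gives the two separate columns.

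**3. The plan's own precision figure.** With mean 80%, SD 6% and n = 12 (SAP 3.1), the normal half-width is 1.96 × 6/√12 = 3.39, giving 76.6% to 83.4%. This reproduces the stated interval of about 77% to 83%. The t-based half-width (11 df) is 2.201 × 6/√12 = 3.81, giving 76.2% to 83.8%. I use 3.81 as the yardstick because the planned test is a t-test.

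**4. Effect of the cut-off on TTR.** The documents give no first-day fall in TTR, so I assume a fall d of 5% to 30%. Take a true reduction of 80%, with the baseline averaging three valid values and one stray value:

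calculated reduction = 1 − 0.20 / ((3 + 1 − d)/4)

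| d | That patient | Shift in mean if 1 of 12 is affected |
|---|---|---|
| 5% | 79.75% | 0.02 points |
| 10% | 79.49% | 0.04 points |
| 20% | 78.95% | 0.09 points |
| 30% | 78.38% | 0.14 points |

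If the list were also taken literally, so that two valid values are averaged with one stray value, the patient's figure would be 79.66% to 77.78% and the shift in the mean 0.03 to 0.19 points. Every shift is towards a smaller reduction.

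**5. Effect of the list on TTR.** Suppose the Day 0 predose value were dropped, and assume a within-patient CV of 5% to 15%. Assume also that the SD of 6 already reflects a three-sample baseline. At an 80% reduction, baseline error enters the percent reduction with factor 20:

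SD = √(36 + (20 × CV)² × (1/2 − 1/3))

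This gives 6.01 (CV 5%), 6.06 (10%) and 6.12 (15%), with half-widths of 3.82, 3.85 and 3.89 instead of 3.81. To first order there is no bias.

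**6. Vitamin A.** Under the list alone, no scheduled value qualifies. Under the Day 1 cut-off, a stray value carries weight 1/2 rather than 1/4, because only one predose sample is scheduled:

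calculated reduction = 1 − 0.20 / ((1 + 1 − d)/2)

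This gives 79.49%, 78.95%, 77.78% and 76.47% for d = 5%, 10%, 20% and 30%. The 80% is illustrative: protocol 1.5.3 reports reductions above 80% for another TTR-targeting product.

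**The case against.** The best defence is that the general rule settles the matter. A value drawn after the Day 0 dose is not a predose value, whatever the parenthesis says, and the Day 0 predose sample plainly is one. Naming a visit with no sample does no harm, since an average uses the values that exist. No TTR or vitamin A sample is scheduled between the first two doses, so the cut-off needs an unplanned draw in a gap of about one day. Vitamin A is not among the endpoints in SAP 1.2.5, and the laboratory list in SAP 4.5.4 does not name it. The plan's rounded interval also implies a half-width nearer 3 points than 3.8.

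All of this limits the size of the problem, and I accept it on that footing. It does not remove the contradiction. The SAP is the programming specification, and the parenthesis is worded as what the rule means. To reach the right answer, the programmer must recognise that part of the sentence is wrong and ignore it.

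Table 1 is dense, so the column positions deserve care. The body weight row (marked at Screening and Predose) and the vitamin B12 row (Screening only) align sensibly in the same columns. The cut-off error does not depend on the table.

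**Conclusion.** The point holds, as a minor one. SAP 3.4 contradicts the day numbering of SAP 3.2 and protocol 6.5, the sampling schedule in Table 1, and its own general rule.

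For the primary analysis the consequence is negligible. The mean moves by at most about 0.2 points in the conservative direction, even under the most literal reading and with one affected patient in 12. The loss of precision from dropping one baseline sample is at most 0.08 points of half-width (3.89 − 3.81). These sizes rest on assumed first-day falls of 5% to 30% and within-patient CVs of 5% to 15%, none of which the documents give.

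The clearest consequence is for vitamin A, which has no scheduled baseline value if the list is followed as written. Nothing here alters the sample-size statement or threatens the primary conclusion.

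**What to change.** Replace only the second sentence of SAP 3.4 with:

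> For TTR and vitamin A, baseline is the average of all values collected before the first dose on Day 0 (TTR: Screening/Baseline, Baseline and Day 0 predose; vitamin A: Day 0 predose), including any unscheduled values before that dose.

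Leave the first sentence of 3.4 and the replicate-averaging rule in 3.2 as they are. SAP 3.11 needs no change, since it already refers to 3.4. The cost is one sentence of SAP text, with no new data and no change to any design figure or study procedure.

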### **3.5.** Methods of Pooling Data

Pooling of data is not applicable to this study.

### **3.6.** Adjustments for Covariates

No statistical analyses that adjust for any covariate(s) are planned.

### **3.7.** Multiple Comparisons/Multiplicity

Not applicable.

### **3.8.** Subpopulations

No analyses of patient subgroups are planned.

### 3.9. Withdrawals, Dropouts, Loss to Follow-up

Patients who withdraw before month 6 or have a dose reduction before 6 months of study participation may be replaced.

### 3.10. Missing Data

In general, there will be no substitutions made to accommodate missing data points. All data recorded on the electronic case report form (eCRF) will be included in data listings that will accompany the CSR. Data collected at multiple time points throughout the study will be presented in chronological order in the data listings according to assessment date/time. Data summaries and analyses will be based on observed data only.

Methods for handling incomplete or missing components of efficacy endpoints are discussed in the endpoint scoring algorithms in Section 6.

## 3.11. Visit Windows

It is expected that all visits should occur according to the protocol schedule. All data will be tabulated per the evaluation visit as recorded on the eCRF even if the assessment is outside of the visit window.

Data collected at unscheduled visits will be included in by-patient data listings, but no assignment to a study visit will be made for the purpose of by-visit summary tabulations. However, unscheduled visits will be considered for computation of baseline values, as discussed in Section 3.4, and for inclusion in any categorical shift summaries (e.g., shift from baseline to "worst" post-baseline value).

The relative day of all dates will be presented in data listings.

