- ^g The preferred region of SC injection is the abdomen; optional additional regions include the upper arm or thigh. The site of injection within a given region will be rotated and recorded. Refer to Section 6.5 for details on study drug administration, including administration at home by a healthcare professional or self or caregiver administration. Patients (or caregivers) administering study drug will be contacted at least once per month by the clinical study center staff to assess AEs, concomitant medications, and to confirm pregnancy testing is being performed.

^h Prior immunosuppressive agent administration and blood levels from the 6 months before signing of the ICF will be collected, if available.

- ⁱ A pregnancy test will be performed for WOCBP only. A serum pregnancy test will be performed at Screening and urine pregnancy tests at all study visits thereafter (W4, W8, W12, W16, W20, W24, W28, W32, W36, W40, W44, W48, W52, W56, W60, W64, W68, W72, and W76) and any time pregnancy is suspected. The results of the pregnancy test must be known before study drug administration.
- ^j Coagulation assessments include PT, aPTT, and INR.
- ^k Blood samples for antidrug antibody testing must be collected before study drug administration. A sample will be collected at the Early Termination visit, if applicable.
- ¹ Blood samples for TTR analysis should be obtained within 1 hour predose.
- ^m Blood sample for TTR analysis should be collected at Week 18 and Week 24 only.
- ⁿ Blood sample for TTR analysis should be collected at Week 57 only.
- ^o Where permitted per local regulations and IRB/IEC approval, blood samples for long-term storage to permit testing of additional proteins related to FAP will be collected.
- ^p Blood samples for plasma PK analysis will be collected predose and 2.5±1 hours postdose.
- ^q Immunosuppressive agent monitoring will be analyzed locally. Unscheduled assessments may be performed if clinically indicated per local standard of care.
- ^r The NIS (weakness, reflexes, and sensation) will be assessed at Screening to determine the likelihood that a patient will meet NIS eligibility criteria at the Screening/Baseline visit; a NIS of 5-130 [inclusive] must be met at the Screening/Baseline visit. The documented results of previously performed NIS assessments may be used at Screening if these tests were performed within 60 days before the date of informed consent.

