1.2.5. Efficacy, Pharmacokinetic, Safety and Exploratory Endpoints

#### 1.2.5.1. Primary Endpoint

The primary endpoint is the percent reduction from baseline in serum TTR level at 6 months.

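### A patient with no Week 26 TTR result leaves the primary analysis even when the scheduled Week 24 sample, at the edge of the Month 6 window, is in hand

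*SAP*

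**What the plan says.** - **Endpoint.** SAP 1.2.5.1: "The primary endpoint is the percent reduction from baseline in serum TTR level at 6 months". Protocol 3.4.1 agrees.
- **Who is analysed.** SAP 2.1 limits the Evaluable Analysis Set to treated patients who "have a non-missing serum TTR result at Month 6 (Week 26) visit". Protocol 10.2.1 sets the same condition, and SAP 4.3.1 bases the primary analysis on this set.
- **Missing values.** SAP 3.10: "In general, there will be no substitutions made to accommodate missing data points". Analyses use observed data.
- **Visit assignment.** SAP 3.11: "All data will be tabulated per the evaluation visit as recorded on the eCRF even if the assessment is outside of the visit window". For unscheduled samples, "no assignment to a study visit will be made for the purpose of by-visit summary tabulations".
- **Sampling.** For the dosing weeks between the Week 12 and Week 26 visits, Protocol Table 1 footnote m says: "Blood sample for TTR analysis should be collected at Week 18 and Week 24 only". Footnote l places TTR draws within an hour before dosing. Footnote c allows 14 days either side for visits after Month 2, and 2 days either side for weekly dosing.
- **Other uses of TTR.** SAP 4.3.2 summarises and plots serum TTR across scheduled visits, for both the Evaluable and the Safety Analysis Sets.
- **Sensitivity analyses.** Protocol 10.2.3.1 promises analyses that vary the handling of missing data. SAP 4.3.1 lists a bootstrap interval for the median and a Wilcoxon signed rank test.

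**The concern.** Two patients can be treated in opposite ways without a stated reason. One has a valid predose sample on Day 168, inside the Month 6 visit window, but missed the Week 26 draw. That patient is out of the primary analysis. The other has only a sample labelled Month 6 that was drawn well outside the window. That patient is in.

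With about 12 patients planned, each one lost is noticeable. Precision falls a little. The larger issue is selection, because patients without a Week 26 draw may differ from those with one, and the SAP contains no analysis that would show whether this matters. Replacement does not close the gap: Protocol 4.4 and SAP 3.9 allow it for withdrawal or dose reduction before 6 months, and do not mention a missed sample.

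**Working it through.** **1. Where the samples fall** (Day 0 is the first dose; 7 days per week)

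- Week 26: 26 × 7 = Day 182. Window: 182 − 14 = Day 168 to 182 + 14 = Day 196.
- Week 24: 24 × 7 = Day 168, exactly the lower limit.
- With the 2-day dosing tolerance, the Week 24 draw falls on Days 166 to 170. Days 168 to 170 are inside the Month 6 window; Days 166 and 167 are one or two days before it.

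Both samples are taken predose and assayed by the same central-laboratory ELISA (Protocol 8.1). They differ nominally by 14 days.

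**2. What the rules do with each pattern**

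| TTR results available | Primary analysis |
|---|---|
| Week 26 label, Days 168 to 196 | Included |
| Week 26 label, outside Days 168 to 196 | Included (SAP 3.11) |
| Week 24 only | Excluded (SAP 2.1, 3.10); still in the SAP 4.3.2 summaries on the Safety Analysis Set |
| Neither | Excluded |

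**3. The plan's own interval**

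Inputs from SAP 3.1: n = 12, mean 80%, SD 6%.

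- Normal: 1.96 × 6/√12 = 3.39, giving 76.6 to 83.4. This reproduces the stated 77 to 83.
- t with 11 df: half-width 3.81, giving 76.2 to 83.8.

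**4. Cost of losing patients**

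Half-width = t(0.975, n−1) × 6/√n, with the SD held at 6%:

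| n | Half-width (points) |
|---|---|
| 12 | 3.81 |
| 11 | 4.03 |
| 10 | 4.29 |
| 9 | 4.61 |

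Recovering one patient to return to 12 saves 4.03 − 3.81 = 0.22 points. Recovering two saves 4.29 − 3.81 = 0.48 points, or 0.48/4.29 = about 11%.

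**5. The test**

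t = 80/(6/√n) is 46.2 at n = 12, 42.2 at n = 10 and 37.7 at n = 8. The conclusion does not depend on one or two patients.

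**6. How often**

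The documents give no rate of missed Week 26 samples. Assuming independent misses at 5%, 10% or 20%, the expected number among 12 is 0.6, 1.2 or 2.4, and the chance of at least one, 1 − (1 − p)^12, is 46%, 72% or 93%. The fallback helps only those who also have a Week 24 result, so these are upper bounds on its use.

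**7. The sensitivity analyses**

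The bootstrap interval and the Wilcoxon test change the statistic, not the patients. By definition no Month 6 TTR value is missing inside the Evaluable Analysis Set, so a missing-data analysis confined to that set has nothing to act on. It needs a wider set.

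**The case against.** Analysis by nominal visit is prespecified, unambiguous and common. The label rule keeps patients in, since a late draw still counts. Timing stays visible because relative days and all protocol deviations are listed (SAP 3.11, 2.2). Patients who stop drug are encouraged to stay for assessments (Protocol 4.3), and those who withdraw before 6 months may be replaced. What remains is a small group: Week 24 present, Week 26 absent despite a generous window. Week 24 also recovers nobody who left earlier. All of this stands, and it keeps the point minor.

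Two stronger readings are tempting, and the documents do not support them.

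- A reader might infer that the Week 24 sample is collected and then ignored. It is not: SAP 4.3.2 covers TTR at each scheduled visit. It is unused only for the primary endpoint.
- A reader might infer that SAP 3.11 causes the loss of patients. It does not. The loss comes from the set definition in SAP 2.1 together with SAP 3.10. SAP 3.11 only adds the contrast, by accepting samples of any date.

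A strict day window is not the remedy either. Requiring a result in Days 168 to 196 would exclude a patient drawn on Day 198 with no Week 24 sample, who is included now. Taking the sample closest to Day 182 would let a Week 24 draw on Day 170 (12 days away) displace a valid Week 26 draw on Day 195 (13 days away).

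**Conclusion.** The point holds as a minor one. The plan drops from its primary analysis any patient who has the Week 24 result but no Week 26 result, and it names no analysis that would show the effect. Under the planning SD the cost is about 0.2 points of half-width for one such patient and 0.5 for two. The number of such patients is unknown.

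It would go too far to say that the efficacy conclusion is in danger: under the planning assumptions the t statistic stays above 37 even with 8 patients. The interval is where the loss shows, and Protocol 10.2.3.1 makes the interval the primary analysis.

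The fallback assumes that a predose value two weeks earlier is an acceptable Month 6 value. The matching sampling conditions and the protocol's own visit window make that reasonable, but neither document states that TTR is constant between Weeks 24 and 26. The gap in missing-data sensitivity analyses is plain from the text and depends on no such assumption.

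**What to change.** 1. In SAP 4.3.1, keep the Week 26-labelled sample as the Month 6 value whenever it exists. When it is missing, use the Week 24 predose sample, accepted within the 2-day dosing tolerance (Days 166 to 170). Amend the Evaluable Analysis Set in SAP 2.1 to count such patients. This rule can only add patients.
2. If the set is to stay as it is, run the same rule as a named sensitivity analysis on all treated patients with a Week 24 or Week 26 TTR result. Either route would give the SAP a rule for missing Month 6 values; this one also supplies the missing-data sensitivity analysis that Protocol 10.2.3.1 promises.
3. Add a sensitivity analysis in which a Week 26 sample drawn outside Days 168 to 196 is replaced by the Week 24 value where there is one. Exclude nobody for an out-of-window draw.

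The cost is a few lines of text and programming; relative study days are already derived (SAP 3.2). Protocol 10.2.1 also defines the Evaluable Analysis Set, so option 1 departs from the protocol and should be recorded under SAP Section 5. Option 2 avoids this. The downside is that a few Month 6 values would come from about two weeks earlier; the report should say how many.
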